7.6.2.3 To assess neurocognitive development and behavior

Neurocognitive development and behavior changes will be assessed based on BSID-III and/or ABAS-3. BSID-III include 5 domains: cognition; language (expressive and receptive); motor (fine and gross motor functioning); and social, emotional, and adaptive behavior. The ABAS-3 assesses up to 11 skill areas: communication, community use, functional academics, health and safety, home or school living, leisure, motor, self-care, self-direction, social, and work (for details refer to Table 7). These raw scores and composite scores will be summarized descriptively. Use Normative and Conversion Tables in Bayley–III Administration Manual to derive scale score and composite score. Raw score, scaled score and composite scores will be presented in listing.

		Max Value		Scaled	
Domain	# of	of Total	Raw	Score[\$]/	Composite
Sub-skill	Questions	Raw Score	Score	Range	Score
1. Cognition	91	91	Y	Y/1-19	Y
2. Language	97	97	Y	Sum/2-38	Y
2.1) Expressive	49	49	Y	Y/1-19	N/A
2.2) Receptive	48	48	Y	Y/1-19	N/A
3. Motor	138	138	Y	Sum/2-38	Y
3.1) Fine	66	66	Y	Y/1-19	N/A
3.2) Gross	72	72	Y	Y/1-19	N/A
4. Social-emotional	35	175	Y	Y/1-19	Y
5. Adaptive behavior (GAC)		723	Y	Sum	Y
5.1) Conceptual		219	Y	N/A	N/A
➤ *Communication (Com)	25	75	Y	Y	N/A
Functional Pre-Academics (FA)	23	69	Y	Y	N/A
➤ *Self-Direction (SD)	25	75	Y	Y	N/A
5.2) Social		138	Y	N/A	N/A

Table 71. Domains for BSID-III/ABAS-3

Statistical Analysis Plan Protocol Number: XPF-009-302 Version: Final 1.0 Date: 04MAY2023 Page 35 of 47

Statistical Analysis Plan (SAP) 🛛 🎇 🗙 E N O N

		Max Value		Scaled	
Domain	# of	of Total	Raw	Score[\$]/	Composite
Sub-skill	Questions	Raw Score	Score	Range	Score
➤ *Leisure (LS)	22	66	Y	Y	N/A
➤ *Social (Soc)	24	72	Y	Y	N/A
5.3) Practical		285	Y	N/A	N/A
Community Use (CU)	22	66	Y	Y	N/A
Home Living (HL)	25	75	Y	Y	N/A
*Health and Safety (HS)	24	72	Y	Y	N/A
➤ *Self-Care (SC)	24	72	Y	Y	N/A
5.4) *Motor (MO)	27	81	Y	Y	N/A

* For children younger than one year, the GAC and composite scores are calculated using only those skill areas indicated by an asterisk (*).

[\$] Sum refers to sum of scaled score of all sub-skills for the specified domain.

The observed and change from OLE baseline values in total raw score and composite score will be summarized for each domain of BSID-III and each skill areas/total scores for ABAS-3 for the scheduled visits by treatment group. Additionally, a box-plot will be given for the observed values at each scheduled visits.

7.6.2.4 To evaluate the investigator's global impression change (CGI-C)

Change over time in subject's seizures and overall condition will be assessed using an investigator-assessed CGI-C scale. Response to CGI-C scale category will be summarized at each of the scheduled visits. Individual listing will be provided for CGI-C score.

7.6.2.5 Rescue medication usage

Seizure rescue therapy details will also be summarized using frequency tables.

Listings will also be provided for seizure rescue therapy details.

7.6.2.6 To assess the impact of XEN496 on the quality of life

The PedsQL is a modular instrument designed to measure health-related quality of life in both healthy and chronically ill children. The scales include parent-reported measures of the child's physical functioning, physical symptoms, emotional functioning, social functioning, and cognitive functioning. Refer appendix 1 for domain scoring details.

The observed values and change from OLE baseline values for each domain and overall scores will be summarized descriptively for each scheduled visits by treatment groups and age group.

[figure not shown]
Listings will be provided for individual PedsQL Inventory scale score.

The PedsQL-FIM was designed to evaluate the impact of pediatric chronic health conditions on parents and the family including measures of parent self-reported physical, emotional, social and cognitive function, communication and worry, in addition to family daily activities and familfy. Refer to appendix 2 for domain scoring details.

[figure not shown]
Statistical Analysis Plan (SAP) 🛛 🏾 🎖 🗶 🛯 N 🔿 N

Observed and change from OLE baseline in PedsQL-FIM for each domain and total score will be summarized descriptively for each scheduled visits.

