Appendix 1: Pediatric Quality of Life (PedsQL) Inventory scale score

DESCRIPTION OF THE QUESTIONNAIRE (INFANTS 1-12 MONTHS):

Dimensions	Number of Items	Cluster of Items	Reversed Scoring	Direction of Dimensions
Physical Functioning	6	1-6	1-6	
Physical Symptoms	10	1-10	1-10	
Emotional Functioning	12	1-12	1-12	Higher scores indicate better HRQOL.
Social Functioning	4	1-4	1-4	_
Cognitive Functioning	4	1-4	1-4	_

DESCRIPTION OF THE QUESTIONNAIRE (INFANTS 13-24 MONTHS):

Dimensions	Number of Items	Cluster of Items	Reversed Scoring	Direction of Dimensions
Physical Functioning	9	1-9	1-9	
Physical Symptoms	10	1-10	1-10	
Emotional Functioning	12	1-12	1-1 2	Higher scores indicate better HRQOL.
Social Functioning	5	1-5	1-5	_
Cognitive Functioning	9	1-9	1-9	_

SCORING OF DIMENSIONS:

Item Scaling	5-point Likert scale from 0 (Never) to 4 (Almost always)	
Weighting of Items	No	
Extension of the Scoring Scale	Scores are transformed on a scale from 0 to 100.	

Statistical Analysis Plan (SAP) 🛛 💥 🗶 E N O N

	Step 1: Transform Score
	Items are reversed scored and linearly transformed to a 0-100 scale as follows: 0=100, 1=75, 2=50, 3=25, 4=0.
	Step 2: Calculate Scores
	Score by Dimensions:
Scoring	 If more than 50% of the items in the scale are missing, the scale scores should not be computed.
Procedure	 Mean score = Sum of the items over the number of items answered.
	Psychosocial Health Summary Score = Sum of the items over the number of items answered in the Emotional, Social, and Cognitive Functioning Scales.
	Physical Health Summary Score = Sum of the items over the number of items answered in the Physical Functioning and Physical Symptoms Scales.
	Total Score: Sum of all the items over the number of items answered on all the Scales.
Interpretation and Analysis	If more than 50% of the items in the scale are missing, the Scale Scores should not be computed.
of Missing Data	If 50% or more items are completed: Impute the mean of the completed items in a scale.

DESCRIPTION OF THE QUESTIONNAIRE (Ages 2-4 year)

Dimensions	Number of Items	Cluster of Items	Reversed Scoring	Direction of Dimensions
Physical Functioning	8	1-8	1-8	
Emotional Functioning	5	1-5	1-5	Higher scores indicate
Social Functioning	5	1-5	1-5	better HRQOL.
School Functioning	3	1-3	1-3	

SCORING OF DIMENSIONS:

Item Scaling	5-point Likert scale from 0 (Never) to 4 (Almost always)				
Weighting of Items	No				

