Extension of the Scoring Scale	Scores are transformed on a scale from 0 to 100.				
Scoring Procedure	Step 1: Transform Score				
	Items are reversed scored and linearly transformed to a 0-100 scale as follows: 0=100, 1=75, 2=50, 3=25, 4=0.				
	Step 2: Calculate Scores				
	 Score by Dimensions: If more than 50% of the items in the scale are missing, the scale scores should not be computed. Mean score = Sum of the items over the number of items answered. 				
	Psychosocial Health Summary Score = Sum of the items over the number of items answered in the Emotional, Social, and School Functioning Scales.				
	Physical Health Summary Score = Physical Functioning Scale Score				
	Total Score: Sum of all the items over the number of items answered on all the Scales.				
Interpretation and Analysis	If more than 50% of the items in the scale are missing, the Scale Scores should not be computed.				
of Missing Data	If 50% or more items are completed: Impute the mean of the completed items in a scale.				

DESCRIPTION OF THE QUESTIONNAIRE (Ages 5-7 year)

Dimensions	Number of Items	Cluster of Items	Reversed scoring	Direction of Dimensions	
Physical Functioning	8	1-8	1-8	N .	
Emotional Functioning	5	1-5	1-5	Higher scores indicate better HRQOL.	
Social Functioning	5	1-5	1-5		
School Functioning	5	1-5	1-5	_	

SCORING OF DIMENSIONS:

Item Scaling	5-point Likert scale from 0 (Never) to 4 (Almost always) 3-point scale: 0 (Not at all), 2 (Sometimes) and 4 (A lot) for the Young Child (ages 5-7) child report
Weighting of Items	No
Extension of the Scoring Scale	Scores are transformed on a scale from 0 to 100.
Scorin g Procedure	Step 1: Transform Score Items are reversed scored and linearly transformed to a 0-100 scale as follows: 0=100, 1=75, 2=50, 3=25, 4=0. Step 2: Calculate Scores Score by Dimensions: • If more than 50% of the items in the scale are missing, the scale scores should not be computed, • Mean score = Sum of the items over the number of items answered. Psychosocial Health Summary Score = Sum of the items over the number of items answered in the Emotional, Social, and School Functioning Scales. Physical Health Summary Score = Physical Functioning Scale Score Total Score: Sum of all the items over the number of items answered on all the scales.

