Interpretation and Analysis of Missing Data	If more than 50% of the items in the scale are missing, the Scale Scores should not be computed. If 50% or more items are completed: Impute the mean of the completed items in a scale.

Note: Domain scores physical functioning, physical symptoms, emotional functioning, social functioning, cognitive and school functioning need to be derived according to the age group where applicable.

Appendix 2: Pediatric Quality of Life Inventory- Family Impact scale (PedsQL-FIM) DESCRIPTION OF THE FAMILY IMPACT MODULE:

Dimensions	Number of Items	Cluster of Items	Reversed Scoring	Direction of Dimensions
Physical Functioning	6	1-6	1-6	Higher scores indicate better functioning.
Emotional Functioning	5	1-5	1-5	
Social Functioning	4	1-4	1-4	
Cognitive Functioning	5	1-5	1-5	
Communication	3	1-3	1-3	
Worry	5	1-5	1-5	
Daily Activities	3	1-3	1-3	
Family Relationships	5	1-5	1-5	

SCORING OF DIMENSIONS:

Item Scaling	5-point Likert scale from 0 (Never) to 4 (Almost always)				
Weighting of Items	No				
Extension of the Scoring Scale	Scores are transformed to a 0 to 100 scale.				
Scoring Procedure	Step 1: Transform Score Items are reversed scored and linearly transformed to a 0-100 scale as follows: 0=100, 1=75, 2=50, 3=25, 4=0 Step 2: Calculate Scores by Dimensions • If more than 50% of the items in the scale are missing, the scale scores should not be computed, • Mean score = Sum of the items over the number of items answered. Step 3: Total Scores • The Total Score is the sum of all 36 items divided by the number of items answered • The Parent HRQL Summary Score (20 items) is computed as the sum of the items divided by the number of items answered in the Physical, Emotional, Social, and Cognitive Functioning scales. • The Family Functioning Summary Score (8 items) is computed as the sum of the items divided by the number of items answered in the Daily Activities and family Relationships scales.				
Interpretation and Analysis of Missing Data	If more than 50% of the items in the scale are missing, the Scale Scores should not be computed. If 50% or more items are completed: Impute the mean of the completed items in a scale.

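### PedsQL total and summary change from OLE baseline can reflect the change of form at age 2, and GAC raw change may compare 7 skill areas with 10

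*SAP*

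**What the plan says.** SAP section 7.6.2.6 states: "The observed values and change from OLE baseline values for each domain and overall scores will be summarized descriptively", to be shown "for each scheduled visits by treatment groups and age group". OLE baseline is a single value, the last non-missing one before the first OLE dose (section 6.1, derived-variables table). Treatment is planned to last about 36 months (section 3.3).

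Appendix 1 scores four PedsQL forms: 1-12 months, 13-24 months, 2-4 years and 5-7 years. On the two infant forms, the Physical Health Summary averages the items "answered in the Physical Functioning and Physical Symptoms Scales". On the two older forms the rule is "Physical Health Summary Score = Physical Functioning Scale Score". The appendix closes by saying that domain scores "need to be derived according to the age group where applicable". No visible text says what to do when the baseline and the later score come from different forms.

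For development, section 7.6.2.3 states: "The observed and change from OLE baseline values in total raw score and composite score will be summarized for each domain of BSID-III". A footnote to the domain table in that section limits the GAC and composite scores of children younger than one year to the asterisked skill areas.

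**The concern.** A change score is meaningful only if both ends measure the same thing. At age 2 two PedsQL scales disappear and one appears, so scores with the same name are built from different content before and after. The planned subtraction can then show improvement or decline in a child whose condition has not moved. The GAC raw total raises a similar question at the first birthday, when skill areas that were not counted at baseline may enter the sum.

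The study has no concurrent control in the open-label period and expects up to about 40 subjects. A few such pairs could move a cell mean, and the table would give the reader no sign of it.

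**Working it through.** **The plan's own figure.** The domain table gives a GAC maximum raw score of 723. Its parts are Conceptual 75+69+75 = 219, Social 66+72 = 138, Practical 66+75+72+72 = 285 and Motor 81. They sum to 219+138+285+81 = 723, so the figure reproduces.

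**PedsQL inputs.** Items per scale, from Appendix 1:

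| Form | Physical Functioning (PF) | Physical Symptoms (PS) | Emotional | Social | Cognitive | School | Total |
|---|---|---|---|---|---|---|---|
| 1-12 months | 6 | 10 | 12 | 4 | 4 | – | 36 |
| 13-24 months | 9 | 10 | 12 | 5 | 9 | – | 45 |
| 2-4 years | 8 | – | 5 | 5 | – | 3 | 21 |
| 5-7 years | 8 | – | 5 | 5 | – | 5 | 23 |

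**Physical Health Summary, unchanged child, all items answered.** It is (6PF+10PS)/16 on the 1-12 month form, (9PF+10PS)/19 on the 13-24 month form, and PF from age 2. The shifts are:

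- 13-24 months to 2-4 years: PF − (9PF+10PS)/19 = (10/19)(PF − PS). Assumed gaps of −25, −10, 0, +10 and +25 give −13.2, −5.3, 0, +5.3 and +13.2 points.
- 1-12 months to 2-4 years: (10/16)(PF − PS), which is 15.6 points for a 25-point gap.
- 1-12 to 13-24 months: (9/19 − 6/16)(PF − PS) = 0.099(PF − PS), about 2.5 points for a 25-point gap.
- 2-4 to 5-7 years: 0.

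**Total score, unchanged child.** The total is the item-weighted mean of the scale scores. The profiles below are assumed (PF/PS/Emotional/Social/Cognitive), and School is assumed to take the Cognitive score.

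| Profile | 1-12 mo | 13-24 mo | 2-4 yr | 5-7 yr |
|---|---|---|---|---|
| 65/40/60/50/40 | 1870/36 = 51.9 | 2315/45 = 51.4 | 1190/21 = 56.7 | 1270/23 = 55.2 |
| 40/65/60/50/40 | 1970/36 = 54.7 | 2340/45 = 52.0 | 990/21 = 47.1 | 1070/23 = 46.5 |
| 40/70/70/50/20 | 2060/36 = 57.2 | 2330/45 = 51.8 | 980/21 = 46.7 | 1020/23 = 44.3 |
| 50 throughout | 50 | 50 | 50 | 50 |

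From the 13-24 month to the 2-4 year form, the total moves by +5.2, −4.9, −5.1 and 0. From 2-4 to 5-7 years it moves by −1.4, −0.6, −2.3 and 0. From 1-12 to 13-24 months it moves by −0.5, −2.7, −5.4 and 0. In these last two steps the scales stay the same and only their item counts change. At age 2 the content itself changes.

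**GAC raw total.** The seven asterisked areas sum to 75+75+66+72+72+72+81 = 513. The three added later (Functional Pre-Academics, Community Use, Home Living) sum to 69+66+75 = 210, and 513+210 = 723. The points contributed by the added areas alone are 0 if they score zero, 21 at 10% of their maximum, 63 at 30%, 105 at 50% and 210 at most. By sub-domain, the Conceptual maximum goes from 150 to 219 and the Practical maximum from 144 to 285. Social stays at 138.

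**The case against.** **Grouping by age may already deal with it.** Section 7.6.2.6 groups by age, and section 7.4.1 has an age category split exactly at 2 years. If the grouping follows baseline age, children aged 2 or more are free of the age-2 effect and the problem is confined to a labelled younger group. That limits it but does not remove it: within the younger group the subtraction is the same. If the grouping follows age at visit, the older group receives baselines from infant forms.

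**The largest figure concerns a score that section 7.6.2.6 does not name.** The section speaks of domain and overall scores. Whether that includes the Physical Health Summary is open, so only the total-score effect is certain to be in scope.

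**Text that is not available could hold a rule.** The protocol's contents list sections on quality-of-life scales (7.1.5) and on behavior and development (7.1.6), but their text and the visit schedules are not in the public documents. That is a fair caution, and the point claims only that no rule is visible.

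**The GAC part is conditional.** It needs a child under 1 year at OLE baseline, a later assessment after the first birthday, and a footnote that extends to the raw total, which it does not say outright.

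**Stronger readings that the documents do not support.**

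- A reader might take the 1 to 84 month ECG bands in section 7.7.5 as entry ages and count how many children change form or outgrow the 5-7 year form. Those bands apply at each scheduled visit and may not be entry limits. Assessment times are not visible either, so no count can be given.
- A reader might conclude that every change of form invalidates the change score. Between the 2-4 and 5-7 year forms the scales are the same and the Physical Health Summary does not shift at all.
- A reader might think that change in Physical Symptoms, Cognitive or School Functioning would be false across age 2. It would simply be missing, because the scale exists on one side only.

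**Conclusion.** The point holds in a limited form and is minor. For children under 2 at OLE baseline who are assessed after age 2, the planned change in the PedsQL total mixes a change of questionnaire with a change in the child. The same applies to the Physical Health Summary if it is reported. The direction depends on the child's profile. The sizes rest on assumed scale scores and on the form following age at assessment; a child kept on the baseline form would show no such shift.

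The GAC raw-score effect depends on how the footnote is read. The upper figure of 210 is a ceiling, not an expectation.

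Section 7.6.2 makes these endpoints secondary and primarily descriptive, observed values and individual listings are also planned, and no test depends on them. PedsQL-FIM has a single form and is unaffected. GAC composites taken from normative tables do not carry this arithmetic.

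**What to change.** 1. In section 7.6.2.6, exclude pairs of assessments that cross the age-2 form break from the tables of change in summary and total scores. For those children, show observed scores by form, and report change only for Physical, Emotional and Social Functioning, the scales named on all four forms. Label it as cross-form, because item content and counts differ (Emotional Functioning, for example, goes from 12 items to 5). Keep change between the 2-4 and 5-7 year forms, with the same label. Pairs from the 1-12 to the 13-24 month form do not cross the break and can also stay, but need at least that label because the item counts shift. Wording the rule by the form actually completed means that it does not depend on how age group is defined.
2. In section 7.6.2.3, for children under 1 year at OLE baseline, compute GAC raw change on the seven asterisked areas at both visits.

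The cost is SAP wording and some programming, with no new data. The downside is that fewer children contribute to summary and total score change. Those removed still contribute to the three common scales and to the observed values.

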7.7 Safety analyses

Statistical Analysis Plan Protocol Number: XPF-009-302 Version: Final 1.0 Date: 04MAY2023 Page 37 of 47

7.7.2 Clinical laboratory evaluations

Observed and change from OLE baseline clinical laboratory test data will be summarized descriptively for each scheduled visit and presented based on the safety set.

Shift from baseline to post-baseline laboratory findings at each visit in normal range criteria (Low, Normal, High) will also be summarized for chemistry and hematology tests.

The incidence of potentially clinically significant abnormalities (PCSA) for liver function (Table 4) for each scheduled visit will be summarized.

Parameter	PCSA Criteria		
Chemistry	Alanine transaminase (ALT) or Aspartate transferase (AST) >=3x Upper limit of normal (ULN)		
	ALT or AST >=5xULN		
	ALT or AST >=8xULN		
	ALT or AST >=3xULN and <5xULN, with Baseline >=2xULN		
	ALT or AST >=5xULN and <8xULN, with Baseline >=2xULN		
	ALT or AST >=5xULN with Baseline >=2xULN		
	Alkaline Phosphatase >=1.5xULN		
	Total Bilirubin >=2xULN		
	ALT >=3xULN and Total Bilirubin >=2xULN		
	Any Chemistry Test		
Hematology	White blood cells (WBC) <2.0 and >20,000 10 ³ cells/uL		
	Hgb:		

Table 4: Potentially	Clinically	Significant	Abnormality	(PCSA)	Liver	Abnormality
Criteria						

Version: Final 1.0 Date: 04MAY2023 Page 38 of 47

Statistical Analysis Plan (SAP) 🕌 🗙 E N O N

Parameter	PCSA Criteria
	Age 30-60 days: Hgb < 7 g/dL
	Age 61 days to 6 years: Hgb <9 g/dL
	Platelets (PLT) <50 x 10^3 cells/uL
	Any Hematology Test

A listing will be provided for clinical laboratory test data. The listing will include normal ranges and clinical laboratory values that are outside the normal ranges and potentially clinically significant abnormalities will be flagged in the listing.

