1 INTRODUCTION

The purpose of this Statistical Analysis Plan (SAP) is to provide detailed descriptions of the statistical methods, data derivations and data displays for study protocol XPF-009-302 Version 3.0, "An open-label extension study of XEN496 in pediatric subjects with KCNQ2 developmental and epileptic encephalopathy" dated 09 May 2022 for final analysis. The table of contents and templates for the tables, figures and listings (TFLs) will be produced in a separate document.

Any deviations from this SAP will be described and justified in the Clinical Study Report (CSR).

The preparation of this SAP has been based on International Conference on Harmonization (ICH) E3 and E9 guidelines.

2

examinations,

Objectives Endpoints **Primary** To assess the long-term safety and Severity and frequency of adverse • tolerability of XEN496 in pediatric subjects events (AEs) and serious adverse with KCNQ2 developmental and epileptic events (SAEs); clinically significant encephalopathy (KCNQ2-DEE) who had changes in laboratory tests, vital signs, electrocardiograms (ECGs), physical participated in the primary study (XPF-009neurologic 301). and CI

STUDY OBJECTIVES AND ENDPOINTS

Secondary

Secondary	
To evaluate the intra-subject efficacy of XEN496 in reducing seizure frequency compared to prior placebo treatment in pediatric subjects with KCNQ2-DEE who were previously randomized to receive placebo in the primary double-blind Phase 3 study (XPF-009-301).	• Change in monthly countable motor seizure frequency, comparing the first 15 weeks of XEN496 treatment in the open label extension (OLE) study to the seizure frequency reported during treatment in the preceding primary study (XPF-009-301), among only those subjects who were randomized to the placebo arm in the primary study (XPF-009-301). (key efficacy endpoint)
To assess the long-term effect of XEN496 on seizure reduction in pediatric subjects treated with XEN496.	 Change from pre-randomization baseline in the previous study over time based on response categories (<25%, 25 to <50%, 50 to <75%, 75 to <100%, 100%), based on estimated seizure frequency every 3 months during the OLE period. Percent change from baseline in countable motor seizure frequency, relative to pre-randomization baseline of the previous study (XPF-009-301), assessed over time every 3 months during the OLE.

Statistical Analysis Plan

Objectives	Endpoints			

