3 STUDY DESIGN

3.1 General study design

This is a Phase 3, open-label, long-term extension study to evaluate the safety, tolerability, and efficacy of XEN496 administered as adjunctive therapy in pediatric subjects with KCNQ2-DEE who participated in the primary study, XPF-009-301.

Approximately 40 subjects may be included in the study based on the anticipated number of subjects who could roll over from Study XPF-009-301.

Subjects will undergo the following:

- Screening/Baseline period Subjects will undergo eligibility assessment at Visit 22 or early termination in the primary study (XPF-009-301).
- Treatment period 36 months:
 - Blinded transition/titration period
 - Open-label period approximately 35 months.

Subjects who received XEN496 in the primary study will continue to receive XEN496 at the same dose throughout the OLE.

[figure not shown]
Subjects allocated to placebo in the primary study will be required to begin a titration of XEN496 CCI

- CCI
- Taper period CCI
 Subjects who discontinue or complete the study treatment will be required to taper off study drug CCI
 The actual duration of the taper period will depend on the subject's dosage prior to taper.
 - Follow-up Approximately 4 weeks after subjects have tapered off of study drug.

Total study duration per subject is estimated to be 37 months.

The Study Design Schematic is presented in Figure 1.

Figure 1: Study Design Schematic

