6 STATISTICAL CONSIDERATIONS AND ANALYSIS

6.1 Derived Variables

The Table 4 provide the list of derived variables for demographic and baseline characteristics, various duration derivations, drug compliance, baseline derivations and other important derivations applicable for this study. Derived efficacy variables will be provided in Section 6.1.1

Table 4 Derived variables

Variables	Formula			
Demographic and Basel	Demographic and Baseline characteristics			
Age (in months)	integer ((Date of informed consent – Date of birth + 1)/ 30.4375)			
Age (in years)	integer ((Date of informed consent – Date of birth + 1)/ 365.25)			
OLE Baseline	Last non-missing value prior to start of study drug in OLE period i.e, Data collected at visit 22 or early termination (ET) visit in the primary study (XPF-009-301) will be considered. If any unscheduled non-missing value available after visit 22 or ET and before first dose in OLE, unscheduled visit value will be considered as baseline.			
Double blind Baseline	Last non-missing value prior to start of study drug in XPF-009- 301 study			
Derivation of Duration				
Study day at any visit	Date of interest – date of first dose of study drug in OLE +1, if date of measurement is on or after the first OLE dose date, or Date of measurement – first dose date, if date of measurement is prior to the first dose date. No Study Day 0 is defined			
Extent of Exposure (Days)	Date of last study medication intake in OLE – Date of first study medication intake in OLE + 1			
Extent of Exposure (Weeks)	Extent of exposure (days)/7			

[figure not shown]
For the computation of Bayley scores, age will need to be expressed in years, months, and days. The following algorithm can be used to derive these values:

TOTDAYS = ADT – BIRTHDT; AGEYRS = FLOOR (TOTDAYS / 365.25); /* age in years */

[figure not shown]

REMAINDR = TOTDAYS – (365.25*AGEYRS); AGEMTHS = FLOOR(REMAINDR / 30.4375); /* age in months */ AGEDAYS = ROUND(REMAINDR – (30.4375*AGEMTHS)); /* in days */

Visit windows for vitals, ECG, and labs are specified in the Table 5. If there is more than one observation within a visit window, the value closest to the nominal study day will be used. If two values are equidistant from the nominal study day, the later value will be used.

Version: Final 1.0 Date: 04MAY2023 Page 26 of 47

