7 STATISTICAL METHODS

7.1 General statistical conventions

All statistical procedures will be completed using SAS GRID Linux/SAS Studio version 9.4.

Unless otherwise stated, all statistical testing will be two-sided and will be performed using a significance (alpha) level of 0.05. Two-sided 95% confidence intervals (CI) will be provided when relevant.

Continuous variables will be summarized using descriptive statistics, including number of subjects (n), mean, geometric mean (for efficacy endpoints only), first quartile (Q1), median, third quartile (Q3), standard deviation (SD), minimum and maximum.

Categorical variables will be summarized using frequency counts and percentages in each category. The denominator for all percentages will be the number of subjects in that treatment group within the population of interest, unless otherwise noted. Percentages will be rounded to one decimal place.

For summary purposes, baseline will be defined as the last available OLE pre-dose value; all summaries will be presented by treatment group assigned in the double blind study (XPF-009-301) and overall, unless otherwise specified.

➢ XEN496 Only

(Subjects who received XEN496 in the primary study and continue to receive XEN496 at the same dose throughout the OLE)

Placebo to XEN496

(Subjects allocated to placebo in the primary study and received XEN496 in OLE)

> Total

All subject data, will be presented in individual subject data listings. Unless otherwise stated, unscheduled visit results will be included in date/time chronological order, within subject listings only. The treatment group as well as subject's sex and age will be stated on each listing. Unless otherwise stated, data listings will be based on all enrolled set.

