7.4.3 Concomitant medications

Medications will be coded to a preferred term and an Anatomic Therapeutic Classification (ATC) code by using the latest available version of the World Health Organization Drug Dictionary Enhanced (WHODDE).

Concomitant medications: are defined as any medications taken between first dose of study treatment (inclusive) in OLE and last dose of study treatment (including taper period). If any medication started prior to first dose in OLE and are ongoing or ended after first dose in OLE are also considered as concomitant.

Concomitant medications will be summarized descriptively using frequency tables by ATC class 2 and preferred name.

Listing will be provided for concomitant medication.

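### In the visible text of SAP 7.7.2, laboratory PCSA incidence is summarised by scheduled visit, so a PCSA seen only at an unscheduled or non-selected draw can miss the table, and the number of subjects ever affected cannot be derived from it

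*SAP*

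**What the plan says.** Three rules in the SAP bear on this point.

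- **Unit of summary (7.7.2).** "The incidence of potentially clinically significant abnormalities (PCSA) for liver function (Table 4) for each scheduled visit will be summarized". The sentence names liver function, but the criteria table it cites also has hematology rows (white cells, hemoglobin, platelets). The shift table in the same section is also by visit and uses normal-range categories. The rows for any chemistry test and any hematology test appear to pool across tests, not across time.
- **Unscheduled results (7.1).** Unless otherwise stated, "unscheduled visit results will be included in date/time chronological order, within subject listings only". The visible text of 7.7.2 states no exception.
- **Several values in one window (6.1).** Visit windows apply to laboratory data. Where a window holds more than one observation, "the value closest to the nominal study day will be used". The tie rule is: "If two values are equidistant from the nominal study day, the later value will be used".

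There is also a safeguard in 7.7.2: "potentially clinically significant abnormalities will be flagged in the listing". Under 7.8 an independent DSMB reviews safety data periodically.

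**The concern.** The primary objective is long-term safety, and its endpoint includes laboratory changes of clinical significance (SAP section 2; protocol synopsis, Outcome Measures). For rare threshold events, such as ALT at or above 3×ULN with total bilirubin at or above 2×ULN, the useful figure is how many children ever met the criterion over up to 36 months of treatment. The visible text plans no such count. It plans a by-visit table, fed by rules that choose a value by its timing and not by its severity. Repeat and unscheduled draws may be the ones that show an abnormality, and these rules can keep them out.

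The SAP does make an exception for unscheduled values elsewhere. The OLE baseline definition in 6.1 admits an unscheduled value taken after Visit 22 or early termination and before the first OLE dose. An unscheduled draw can therefore set the baseline used in the criteria that require baseline at or above 2×ULN, while an unscheduled post-baseline draw is left to listings under 7.1.

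**Working it through.** The plan gives no figure on this point, so there is nothing to reproduce. The check is to apply the stated rules.

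**Inputs from the documents.** Summary per scheduled visit (7.7.2); unscheduled results in listings unless otherwise stated (7.1); closest to nominal, later if tied (6.1); up to about 40 subjects (section 4).

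**Assumed.** Day offsets, number of laboratory visits and smaller enrolments, because the window table and visit schedules are not visible.

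**Step 1: which draws can reach the table.** The SAP does not say how 7.1 and 6.1 work together.

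- Reading A: 7.1 is strict. A PCSA seen only at an unscheduled draw never reaches the by-visit table.
- Reading B: windowing counts as the stated exception, so unscheduled draws compete for a window. A PCSA that is alone in its window is counted. It is lost only if the window holds two or more draws and the PCSA is only in one that is not kept.

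**Step 2: the 6.1 rule under reading B, one child, N = 40.**

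| Draws (days from nominal) | Value kept | By-visit count | Any-time count |
|---|---|---|---|
| +1 normal, +5 PCSA | +1 normal | 0/40 | 1/40 |
| −3 PCSA, +3 normal | +3 normal (tie, later) | 0/40 | 1/40 |
| +5 PCSA alone | +5 PCSA | 1/40 | 1/40 |
| +1 PCSA, +5 normal | +1 PCSA | 1/40 | 1/40 |

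The first two rows lose the event from the table; the last two do not.

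**Step 3: from by-visit counts to subjects ever affected.** This step does not depend on unscheduled draws. With one event at each of K visits, the number of subjects ever affected lies between 1 (the same child each time) and K (different children).

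- K = 2: 1/40 = 2.5% to 2/40 = 5.0%.
- K = 10 (assumed): 1/40 = 2.5% to 10/40 = 25.0%.

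In both cases the by-visit table reads 1/40 = 2.5% at every visit.

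**Step 4: weight of one child, 100/N percentage points.** N = 40: 2.5. If fewer enrolled (assumed), N = 30: 3.3; N = 20: 5.0; N = 10: 10.0.

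**The case against.** The strongest reply is that much of the relevant text cannot be seen. Under 7.7 only the heading survives. Section 7.7.1, the safety-set definition, the body of protocol 8.3.2 on safety endpoints, the window table and the schedules are also not visible, and the "templates for the tables, figures and listings (TFLs) will be produced in a separate document". A reader might infer that the plan has no any-time count anywhere. The documents do not support that: such a row could stand in any of these places. This part of the objection stands in full and confines the point to the visible text.

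A second reply is that nothing is lost from the report. Unscheduled results stay in the chronological listings, PCSA values are flagged there, and with about 40 subjects someone could count by hand. A reader might infer that abnormal results would go unreported; the flagged listing rules that out. What remains is that a listing, like DSMB review, is not a planned summary with a defined numerator and denominator.

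Third, 7.1 opens with a proviso, and windowing may be meant as the exception. That stands as reading B: it would be wrong to say every unscheduled PCSA is excluded. The loss is then narrower, and its frequency cannot be judged.

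Fourth, PCSA are threshold flags for potential significance. The endpoint concerns changes judged clinically significant, some of which may be captured as adverse events under text not visible here. This loosens the link to the primary endpoint but does not remove it.

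None of these replies answers step 3: by-visit counts alone cannot give the number ever affected.

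**Conclusion.** The point holds for the visible text. The stated rules can leave a PCSA out of the incidence table in 7.7.2, and that table cannot show how many subjects ever met a criterion. The number of children affected is unknown. Each one weighs 2.5 percentage points at 40 subjects, and more if enrolment is smaller. The offsets and visit numbers used above are illustrative.

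The conclusion assumes that no unseen text or table template already supplies an any-time row. If one does, a confirming sentence in 7.7.2 is enough. The consequence is a possibly understated summary, not missing data, so this is a worthwhile correction and not a threat to the study's conclusions.

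**What to change.** In 7.7.2:

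1. Add the number and percent of subjects meeting each chemistry and hematology PCSA criterion at least once post-baseline in the OLE, using all scheduled, unscheduled, repeat and early-termination values, by prior-treatment group and overall.
2. Use as denominator the safety-set subjects with at least one post-baseline value for the parameter.
3. Count over the treatment-emergent period to which 6.2.2 already refers (its definition is not visible), so that the safety tables share one window. Show values from the later follow-up separately; section 3.1 places follow-up "Approximately 4 weeks after subjects have tapered off of study drug".
4. For the combined ALT and total bilirubin criterion, state whether both must occur at the same draw or within a stated interval. Without this, pooling over time could overcount.
5. State the new summary as an exception to the listings-only rule in 7.1, and limit the 6.1 selection rule to by-visit summaries.

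The by-visit table can stay. The cost is SAP wording and one extra table section from data already collected. The one downside is that reported incidence may be slightly higher than in the by-visit table.
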